7.6.8 Interim Analyses

One IA will be performed when a minimum of 22 paired muscle biopsies are completed. A group sequential method (O'Brien-Fleming Spending Function) will be used to ensure an

Fulcrum Therapeutics Losmapimod
 Protocol FIS-002-2019, Version 4.0 (COVID-19 Pandemic Emergency Amendment) 10 April 2020
 overall significance level of 0.05 (double-sided) due to multiple looks at the DUX4 primary endpoint, if the IA is deemed necessary by the Sponsor.

- With a sample size of approximately 22 subjects at IA, the test alpha at IA is approximately 0.001, and the final test alpha is 0.05. If the p-value from the test is <0.001 , then the study may be stopped for efficacy, or continue as planned as decided by the Sponsor. Cumulative exit probability under the alternative hypothesis is approximately 2.3% and approximately 82.3% at the IA and final analysis, respectively (SAS Version 9.4; nQuery 8 – Power and Sample Size for Group Sequential Trials, Version 8.5.1.0).
- With a sample size of 32 subjects at IA, the test alpha at IA is approximately 0.004, and the final test alpha is 0.048. If the p-value from the test is <0.004 , then the trial may be stopped for efficacy, or continue as planned as decided by Sponsor. Cumulative exit probability under the alternative hypothesis is approximately 13.9% and approximately 82.2% at the IA and final analysis, respectively (SAS Version 9.4; nQuery 8 – Power and Sample Size for Group Sequential Trials, Version 8.5.1.0).

The alphas at the time of the IA for sample sizes ranging from 22 to 32 are provided in [Table 7-1](#):

Table 7-1 Alpha at Interim Analysis and Final Analysis for Different Sample Sizes at Interim Analysis (O'Brien-Fleming Method)

Interim Analysis Sample Size	Alpha at Interim Analysis	Alpha at Final
22	0.000567	0.049755
23	0.000736	0.049685
24	0.000951	0.049596
25	0.001203	0.049493
26	0.001474	0.049384
27	0.001803	0.049253
28	0.002173	0.049107
29	0.002556	0.048959
30	0.003005	0.048787
31	0.003496	0.048602
32	0.004027	0.048405

Fulcrum Therapeutics

Protocol FIS-002-2019, Version 4.0 (COVID-19 Pandemic Emergency Amendment)

Losmapimod

10 April 2020

8 Data Quality Assurance

This study will be conducted according to the International Council for Harmonisation (ICH) E6(R2) risk and quality processes described in the applicable procedural documents. The quality management approach to be implemented in this study will be documented and will comply with the current ICH guidance on quality and risk management.

8.1 Data Management

As part of the responsibilities assumed by participating in the study, the investigator agrees to maintain adequate case histories for the subjects treated as part of the research under this protocol. The investigator agrees to maintain accurate eCRFs and source documentation as part of the case histories. These source documents may include laboratory reports, ECG strips, etc.

Study site personnel will enter subject data into Medidata RAVE® (the eCRF program). The analysis data sets will be a combination of these data and data from other sources (eg, laboratory data).

Clinical data management will be performed in accordance with applicable █ standards and data cleaning procedures to ensure the integrity of the data, eg, removing errors and inconsistencies in the data. Adverse event terms will be coded using MedDRA, an internal validated medical dictionary, and concomitant medications will be coded using the World Health Organization Drug Dictionary.

After final database lock, each study site will receive a CD-ROM containing all of their site specific eCRF data as entered into the Medidata RAVE system for the study, including full discrepancy and audit history. Additionally, a CD-ROM copy of all of the study site's data from the study will be created and sent to the sponsor for storage. █ will maintain a duplicate CD-ROM copy for their records. In all cases, subject initials will not be collected or transmitted to the sponsor.

Fulcrum Therapeutics

Losmapimod

Protocol FIS-002-2019, Version 4.0 (COVID-19 Pandemic Emergency Amendment)

10 April 2020

9 Ethics

9.1 Independent Ethics Committee or Institutional Review Board

Federal regulations and the ICH guidelines require that approval be obtained from an IRB/IEC before participation of human subjects in research studies. Before study onset, the protocol, informed consent, advertisements to be used for the recruitment of study subjects, and any other written information regarding this study to be provided to the subject or the subject's legal guardian must be approved by the IRB/IEC. Documentation of all IRB/IEC approvals and of the IRB/IEC compliance with ICH harmonised tripartite guideline E6(R2): Good Clinical Practice (GCP) will be maintained by the site and will be available for review by the sponsor or its designee.

All IRB/IEC approvals should be signed by the IRB/IEC chairman or designee and must identify the IRB/IEC name and address, the clinical protocol by title or protocol number or both, and the date on which approval or a favorable opinion was granted.

The investigator is responsible for providing written summaries of the progress and status of the study at intervals not exceeding 1 year or otherwise specified by the IRB/IEC. The investigator must promptly supply the sponsor or its designee, the IRB/IEC, and, where applicable, the institution, with written reports on any changes significantly affecting the conduct of the study or increasing the risk to subjects.

9.2 Ethical Conduct of the Study

The study will be performed in accordance with the ethical principles that have their origin in the Declaration of Helsinki, ICH GCP, the protocol, and all applicable regulations.

9.3 Subject Information and Consent

A written informed consent approved by the sponsor and by the IEC/IRB in compliance with applicable regulatory authority regulations shall be obtained from each subject before entering the study or performing any unusual or nonroutine procedure that involves risk to the subject. An informed consent template may be provided by the sponsor to investigative sites. If any institution-specific modifications to study-related procedures are proposed or made by the site, the consent should be reviewed by the sponsor or its designee or both before IRB/IEC submission. Once reviewed, the consent will be submitted by the

Fulcrum Therapeutics

Losmapimod

Protocol FIS-002-2019, Version 4.0 (COVID-19 Pandemic Emergency Amendment)

10 April 2020

investigator to his or her IRB/IEC for review and approval before the start of the study. If the ICF is revised during the course of the study, all active participating subjects must sign the revised form.

Before recruitment and enrollment, each prospective subject or his or her legal guardian will be given a full explanation of the study and be allowed to read the approved ICF. Once the investigator is assured that the subject/legal guardian understands the implications of participating in the study, the subject/legal guardian will be asked to give consent to participate in the study by signing the ICF.

The investigator shall retain the signed original ICF(s) and give a copy of the signed original form to the subject or legal guardian.

Fulcrum Therapeutics

Losmapimod

Protocol FIS-002-2019, Version 4.0 (COVID-19 Pandemic Emergency Amendment)

10 April 2020

10 Investigator's Obligations

The following administrative items are meant to guide the investigator in the conduct of the study but may be subject to change based on industry and government standard operating procedures, working practice documents, or guidelines. Changes will be reported to the IRB/IEC but will not result in protocol amendments.

10.1 Confidentiality

All laboratory specimens, evaluation forms, reports, and other records will be identified in a manner designed to maintain subject confidentiality. All records will be kept in a secure storage area with limited access. Clinical information will not be released without the written permission of the subject (or the subject's legal guardian), except as necessary for monitoring and auditing by the sponsor, its designee, applicable regulatory authorities, or the IRB/IEC.

To ensure privacy, directly identifying information of study subjects will not be attached to records or samples released to the sponsor and its service providers for research purposes.

The investigator and all employees and coworkers involved with this study may not disclose or use for any purpose other than performance of the study any data, record, or other unpublished, confidential information disclosed to those individuals for the purpose of the study. Prior written agreement from the sponsor or its designee must be obtained for the disclosure of any said confidential information to other parties. Additional confidentiality requirements and obligations will be set forth in the clinical trial agreement to be entered into by the sponsor, the principal investigator, and the institution.

10.2 Financial Disclosure and Obligations

Investigators are required to provide financial disclosure information to allow the sponsor to submit the complete and accurate certification or disclosure statements required by applicable regulatory authorities. In addition, the investigator must provide to the sponsor a commitment to promptly update this information if any relevant changes occur during the course of the investigation and for 1 year following the completion of the study.

Neither the sponsor nor [REDACTED] is financially responsible for further testing or treatment of any medical condition that may be detected during the screening process. In addition, in the

Fulcrum Therapeutics Losmapimod
Protocol FIS-002-2019, Version 4.0 (COVID-19 Pandemic Emergency Amendment) 10 April 2020
absence of specific arrangements, neither the sponsor nor [REDACTED] is financially responsible for further treatment of the subject's disease.

10.3 Investigator Documentation

Prior to beginning the study, the investigator will be asked to comply with ICH E6(R2) 8.2 and, for US sites, Title 21 of the Code of Federal Regulations by providing the following essential documents, including but not limited to:

- IRB/IEC approval
- Original investigator-signed investigator agreement page of the protocol
- For US sites, Form FDA 1572, fully executed, and all updates on a new fully executed Form FDA 1572
- For non-US sites, the investigator's current curriculum vitae and/or other documentation evidencing qualifications, and any other documents that the IRB/IEC may request. For US sites, a curriculum vitae for the investigator and each subinvestigator listed on Form FDA 1572
- Financial disclosure information to allow the sponsor to submit complete and accurate certification or disclosure statements required by applicable regulatory authorities. In addition, the investigators must provide to the sponsor a commitment to promptly update this information if any relevant changes occur during the course of the investigation and for 1 year after the completion of the study.
- IRB/IEC-approved informed consent, samples of site advertisements for recruitment for this study, and any other written information regarding this study that is to be provided to the subject or legal guardian, and
- Laboratory certifications and normal ranges for any local laboratories used by the site.

10.4 Study Conduct

The investigator agrees that the study will be conducted according to the principles of ICH E6(R2). The investigator will conduct all aspects of this study in accordance with all national, state, and local laws or regulations. Study information from this protocol will be posted on publicly available clinical trial registers before enrollment of subjects begins.

Fulcrum Therapeutics

Protocol FIS-002-2019, Version 4.0 (COVID-19 Pandemic Emergency Amendment)

Losmapimod

10 April 2020

10.5 Adherence to Protocol

The investigator agrees to conduct the study as outlined in this protocol in accordance with ICH E6(R2) and all applicable guidelines and regulations.

10.6 Adverse Events and Study Report Requirements

By participating in this study, the investigator agrees to submit reports of SAEs to the sponsor and/or IRB/IEC according to the time line and method outlined in the protocol. In addition, the investigator agrees to submit annual reports to the study site IRB/IEC as appropriate.

10.7 Investigator's Final Report

Upon completion of the study, the investigator, where applicable, should inform the institution; the investigator/institution should provide the IRB/IEC with a summary of the study's outcome and the sponsor and regulatory authority(ies) with any reports required.

10.8 Records Retention

Essential documents should be retained until at least 2 years after the last approval of a marketing application in an ICH region and until there are no pending or contemplated marketing applications in an ICH region or at least 2 years have elapsed since the formal discontinuation of clinical development of the investigational product. These documents should be retained for a longer period, however, if required by the applicable regulatory requirements or by an agreement with the sponsor. It is the responsibility of the sponsor to inform the investigator/institution as to when these documents no longer need to be retained.

10.9 Publications

After completion of the study, the data will be submitted for reporting at a scientific meeting and for publication in a peer-reviewed scientific journal. In these cases, the sponsor will be responsible for these activities and will work with the investigators to determine how the manuscript is written and edited, the number and order of authors, the publication to which it will be submitted, and other related issues. The sponsor has final approval authority over all such issues.

Fulcrum Therapeutics

Losmapimod

Protocol FIS-002-2019, Version 4.0 (COVID-19 Pandemic Emergency Amendment)

10 April 2020

Data are the property of the sponsor and cannot be published without prior authorization from the sponsor, but data and publication thereof will not be unduly withheld. Further terms concerning publication will be set forth in the clinical trial agreement entered into by the sponsor, the principal investigator, any vendors, and the institution.

Fulcrum Therapeutics

Losmapimod

Protocol FIS-002-2019, Version 4.0 (COVID-19 Pandemic Emergency Amendment)

10 April 2020

11 Study Management

The administrative structure will include an SRC.

11.1 Monitoring

11.1.1 Safety Review Committee

An SRC will be formed to review safety data for all subjects at regular intervals throughout the study.

The SRC charter will describe the processes for unblinding subject- or study-level data if the SRC requests unblinding. Details on the composition of the SRC and the schedule of SRC meetings and data reviews will be presented in the SRC charter.

11.1.2 Monitoring of the Study

The clinical monitor, as a representative of the sponsor, has the obligation to follow the study closely. In doing so, the monitor will visit the investigator and study site at periodic intervals, in addition to maintaining necessary telephone and letter contact. The monitor will maintain current personal knowledge of the study through observation, review of study records and source documentation, and discussion of the conduct of the study with the investigator and personnel.

All aspects of the study will be carefully monitored, by the sponsor or its designee, for compliance with applicable government regulation with respect to current GCP and current standard operating procedures.

11.1.3 Inspection of Records

Investigators and institutions involved in the study will permit study-related monitoring, audits, IRB/IEC review, and regulatory inspections by providing direct access to all study records. In the event of an audit, the investigator agrees to allow the sponsor, representatives of the sponsor, or a regulatory agency (eg, FDA or other regulatory agency) access to all study records.

Fulcrum Therapeutics Losmapimod
Protocol FIS-002-2019, Version 4.0 (COVID-19 Pandemic Emergency Amendment) 10 April 2020
The investigator should promptly notify the sponsor and [REDACTED] of any audits scheduled by any regulatory authorities and promptly forward copies of any audit reports received to the sponsor.

11.2 Management of Protocol Amendments and Deviations

11.2.1 Modification of the Protocol

Any changes in this research activity, except those necessary to remove an apparent, immediate hazard to the subject, must be reviewed and approved by the sponsor or its designee. Amendments to the protocol must be submitted in writing to the investigator's IRB/IEC for approval before subjects can be enrolled into an amended protocol.

11.2.2 Protocol Deviations

The investigator or designee must document and explain in the subject's source documentation any deviation from the approved protocol. The investigator may implement a deviation from or a change of the protocol to eliminate an immediate hazard to study subjects without prior IRB/IEC approval. As soon as possible after such an occurrence, the implemented deviation or change, the reasons for it, and any proposed protocol amendments should be submitted to the IRB/IEC for review and approval, to the sponsor for agreement, and to the regulatory authorities, if required.

A deviation from the protocol is an unintended or unanticipated departure from the procedures or processes approved by the sponsor and the IRB/IEC and agreed to by the investigator. A significant deviation occurs when there is nonadherence to the protocol by the subject or investigator that results in a significant, additional risk to the subject. Significant deviations can include nonadherence to inclusion or exclusion criteria or nonadherence to FDA regulations or ICH GCP guidelines and will lead to the subject being withdrawn from the study ([Section 4.2](#)). A list of major protocol deviations will be compiled prior to the start of the study.

Protocol deviations will be documented by the clinical monitor throughout the course of monitoring visits. Principal investigators will be notified in writing by the monitor of deviations. The IRB/IEC should be notified of all protocol deviations in a timely manner.

Fulcrum Therapeutics

Losmapimod

Protocol FIS-002-2019, Version 4.0 (COVID-19 Pandemic Emergency Amendment)

10 April 2020

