4.2.1 Reasons for Withdrawal/Discontinuation

Subjects may withdraw from the study at any time and for any reason without prejudice to their future medical care by the investigator or at the study site. Every effort should be made to keep subjects in the study, including if a subject decides to prematurely discontinue study treatment. The reasons for subjects not completing the study will be recorded. A subject may be withdrawn from the study for any of the following reasons:

1. The subject does not meet the protocol inclusion or exclusion criteria.
2. The subject is noncompliant with the protocol.
3. The subject has a serious or intolerable AE(s) that, in the investigator's opinion, requires withdrawal from the study.
4. The subject has laboratory safety results that reveal clinically significant hematological or biochemical changes from the baseline values.
5. The subject has symptoms or an intercurrent illness not consistent with the protocol requirements or that justify withdrawal.
6. The subject is lost to follow-up.
7. Other reasons (eg, pregnancy, development of contraindications of use of study drug).

Fulcrum Therapeutics

Losmapimod

Protocol FIS-002-2019, Version 4.0 (COVID-19 Pandemic Emergency Amendment)

10 April 2020

8. The subject withdraws consent, or the investigator or sponsor decides to discontinue the subject's participation in the study.

The investigator will also withdraw a subject if Fulcrum Therapeutics terminates the study. Upon occurrence of a serious or intolerable AE, the investigator will confer with the sponsor. If a subject is discontinued because of an AE, the event must continue to be followed to satisfactory resolution as described in [Section 6.2.1.10](#). Any subject may withdraw his or her consent at any time.

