4.2.2 Handling of Withdrawals

Subjects are free to withdraw from the study or study treatment at any time upon request. Subject participation in the study may be stopped at any time at the discretion of the investigator or at the request of the sponsor.

Subjects who discontinue study treatment or active participation in the study will no longer receive study drug. When a subject withdraws from the study treatment or active participation in the study, the reason(s) for withdrawal shall be recorded by the investigator on the relevant page of the electronic case report form (eCRF).

If a subject prematurely discontinues study treatment, they will be encouraged to remain in the study and continue with all other aspects of the study. If appropriate, subjects can restart study drug at the 7.5 mg PO BID dose at the investigator's discretion (depending on the reason for discontinuation of study treatment), after approval from the sponsor.

If a subject decides to prematurely discontinue study treatment and not continue with all other aspects of the study, they will be considered to have withdrawn from the study. If a subject withdraws from the study, they will be asked to complete the early termination (ET) visit as soon as possible after the decision to terminate study participation and to complete the safety follow-up visit 7 (± 3) days after their last dose of study drug. If the ET visit will be scheduled more than 7 days after the last dose of study drug, the safety follow-up and ET visits may be combined, with no duplication of assessments required.

Subjects who fail to return for final assessments will be contacted by the site in an attempt to have them comply with the protocol. In the case of subjects being lost to follow-up, at least 3 documented attempts to contact the subject must be made.

Fulcrum Therapeutics Losmapimod
Protocol FIS-002-2019, Version 4.0 (COVID-19 Pandemic Emergency Amendment) 10 April 2020
It is vital to obtain follow-up data on any subject withdrawn because of an AE or SAE. In every case, efforts must be made to undertake protocol-specified, safety, follow-up procedures.

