13.1 Appendix: Schedules of Events

Fulcrum Therapeutics

Protocol FIS-002-2019, Version 4.0 (COVID-19 Pandemic Emergency Amendment)

Losmapimod

10 April 2020

Table 13-1 Schedule of Events: Placebo-Controlled Treatment Period

Procedure	Screening	Baseline	Week 4	Week 12	Week 16	Week 24	Week 36	Week 48 End of Placebo- Controlled Treatment Period/Start of OLE ^a	ET Visit ^b	Safety Follow-Up 7 Days After the Last Dose of Study Drug ^c
Visit Number	0	1	2	3	4	5	6	7	-	8
Visit Window (days) ^d	-28 to -1	Day 1	±5	±5	±5	±5	±14 ^{aa}	±5		±3
Informed consent	X									
Confirm eligibility via inclusion/exclusion criteria	X	X								
Randomization		X								
Demographics	X									
Height and BMI ^e	X									
Medical history	X	X ^f								
FSHD-specific history ^g	X									
Serology (HBsAg, HCV, HIV1/HIV2)	X									
Urine drug screen ^h	X									
Genetic confirmation of FSHD1 ⁱ	X									
Serum β-hCG ^k	X									
Serum follicle-stimulating hormone ^l	X									
Urine pregnancy test ^m		X	X	X	X	X	X	X	X	X
Weight ^e	X	X						X	X	X
Vital signs ⁿ	X	X	X	X	X	X	X	X	X	X

Fulcrum Therapeutics

Protocol FIS-002-2019, Version 4.0 (COVID-19 Pandemic Emergency Amendment)

Losmapimod

10 April 2020

Procedure	Screening	Baseline	Week 4	Week 12	Week 16	Week 24	Week 36	Week 48 End of Placebo- Controlled Treatment Period/Start of OLE ^a	ET Visit ^b	Safety Follow-Up 7 Days After the Last Dose of Study Drug ^c
Visit Number	0	1	2	3	4	5	6	7	-	8
Physical examination ^o	X									X
Standard 12-lead ECG ^p	X	X	X					X	X	X
Serum chemistry	X ^q	X	X	X	X	X	X	X	X	X
Hematology	X ^q	X	X	X	X	X	X	X	X	X
Blood sample for coagulation ^{bb}	X ^q						X			
Urinalysis	X							X	X	X
MSK MRI ^r	X			X				X	X ^s	
Muscle needle biopsy ^t		X			X		X ^t			
PK sampling ^u		X	X	X	X	X	X	X	X	
Target engagement sampling ^v		X			X		X			
RWS		X	X	X		X	X	X	X	X
TUG (classic and FSHD)		X	X	X		X	X	X	X	X
Manual dynamometry		X	X	X		X	X	X	X	X
MFM Domain 1		X		X		X	X	X	X	X
FSHD-HI questionnaire		X	X	X		X	X	X	X	X
PGIC questionnaire			X	X	X	X	X	X	X	X
Clinic visit	X	X	X	X	X	X	X	X	X	X
Study drug dispensation ^x		X	X	X	X	X ^y	X	X		
Study drug count		X	X	X	X	X	X	X	X	

Fulcrum Therapeutics

Protocol FIS-002-2019, Version 4.0 (COVID-19 Pandemic Emergency Amendment)

Losmapimod

10 April 2020

Procedure	Screening	Baseline	Week 4	Week 12	Week 16	Week 24	Week 36	Week 48 End of Placebo- Controlled Treatment Period/Start of OLE ^a	ET Visit ^b	Safety Follow-Up 7 Days After the Last Dose of Study Drug ^c
Visit Number	0	1	2	3	4	5	6	7	-	8

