The quantification of gene expression and normalization of qPCR are conducted at a central laboratory (Q2 Lab Solutions) in a blinded fashion, with no access to treatment assignment information. A total of six DUX4-regulated gene transcripts (CCNA1; KHDC1L; MBD3L2; PRAMEF6; SLC34A2; ZSCAN4) have been pre-selected for inclusion in the mean DUX4 score. DUX4 Score 1 will be used for the primary analysis. A second and third composite scores (DUX4 Score 2 and DUX4 Score 3, respectively) will be used for sensitivity analysis. For details on assay validation, gene subset selection criteria/process, and derivation of DUX4 Score, see [Appendices 15.1 – 15.5](#).

DUX4 score 1 will be summarized as change from baseline to either Week 16 or Week 36. Study subjects can only have one post-baseline biopsy (either Week 16 or Week 36, but not both). If the pre-treatment or on-treatment DUX-4 results are unavailable, then the assessment is considered missing. See [Section 8.2.1](#) for details of missing data handling for DUX4 Score.

For each treatment, descriptive statistics of aberrant DUX4 activity will be presented at Baseline and post-baseline (Week 16 or Week 36) as well as change from baseline. An ANCOVA model

will be used to analyze the change from baseline in DUX4 activity in affected skeletal muscle, which is the response variable, with repeat number category and treatment group as fixed effects and baseline DUX4 activity in affected skeletal muscle as a covariate. Within-group least-squares (LS) means, the associated standard errors (SEs) and 2-sided 95% CIs, treatment differences in LS means and the associated 2-sided 95% CIs and 2-sided p-values will be derived from the model and presented in the table. If the model-based p-value of the treatment difference in the change from baseline is less than the final alpha provided in [Table 12-1](#), the difference between two treatment groups will be determined to be statistically significant.

Similar methods will be used to analyze the change from baseline in DUX4 activity within subgroups identified in [Section 4.6](#) to evaluate consistency of treatment effects across the subgroups. For the repeat category subgroup analysis, the repeat category will be excluded as fixed effect from the model.

The LS mean change from baseline by visit of the DUX4 activity will be graphically presented.

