8.2.1. Sensitivity Analyses of Primary Endpoint

Missing Data: The following sensitivity analyses will be conducted on the primary efficacy endpoint to assess the impact of missing data on study conclusions:

- **Last Observation Carried Forward (LOCF):** Post-baseline missing DUX4 score will be imputed using baseline DUX4 score for each subject with missing data. Patients who are missing the baseline assessment will be excluded from the analysis.
- **Placebo Mean Imputation:** Post-baseline missing DUX4 score will be imputed using mean post-baseline score calculated from the placebo arm. Patients who are missing the baseline assessment will be excluded from the analysis.
- **Observed worst case imputation:** For subjects with missing baseline DUX4, imputation will be done using the smallest baseline DUX4 score among subjects with non-missing data. For subjects missing post-baseline DUX4, imputation will be done using the highest DUX4 score among subjects with non-missing data.

DUX4 by timepoint: The primary endpoint will be analyzed separately for Week 16 and Week 36 to assess the impact of biopsy timing on study conclusions.

COVID-19 related treatment disruptions: Subjects may be diagnosed with COVID-19 and proceed on a quarantine or have no access to study treatment for a prolonged duration. These subjects will be excluded from analysis of the primary endpoint, to assess the impact of COVID-19 related treatment disruptions on the study conclusions.

Excluding cross-over subjects: Subjects who already transitioned into open label losmapimod based on the prior protocol version will be excluded from the analysis.

DUX4 change excluding subjects with censored laboratory observations at baseline:
Subjects with censored observations at baseline for any of the transcripts in the panel of 6 DUX4-regulated transcripts will be excluded from the analysis.

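### Protocol 11.2.2 makes study withdrawal mandatory for significant deviations where 4.2.1 leaves it discretionary; if applied before the Week 16/36 biopsy, it costs that subject's primary outcome

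*Protocol*

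**What the plan says.** Protocol 11.2.2 defines a significant deviation as nonadherence, by the subject or the investigator, that "results in a significant, additional risk to the subject". Its examples are breaches of the eligibility criteria, FDA regulations or GCP. It says that such deviations "will lead to the subject being withdrawn from the study" and refers to Section 4.2.

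In that section, Protocol 4.2.1 is permissive: "A subject may be withdrawn from the study for any of the following reasons". The first two listed reasons are failing the eligibility criteria and being noncompliant. The same paragraph says: "Every effort should be made to keep subjects in the study, including if a subject decides to prematurely discontinue study treatment". Protocol 4.2.2 says of subjects who stop study drug early that "they will be encouraged to remain in the study and continue with all other aspects of the study". A subject who leaves the study is asked for an early termination (ET) visit and a safety follow-up visit. Under 4.2.3, no one is replaced.

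In Protocol Table 13-1 the row "Muscle needle biopsy" is marked at baseline, Week 16 and Week 36, and not at ET or safety follow-up. SAP 8.2 adds: "If the pre-treatment or on-treatment DUX-4 results are unavailable, then the assessment is considered missing". It allows one post-baseline biopsy per subject. Imputation appears only in SAP 8.2.1, introduced by "The following sensitivity analyses will be conducted on the primary efficacy endpoint to assess the impact of missing data on study conclusions".

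**The concern.** A site that follows the cross-reference from 11.2.2 goes from a mandatory instruction to a discretionary one for overlapping triggers. The stricter rule acts after randomisation. For a subject not yet biopsied, it removes the only measurement that the primary analysis can use.

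The analysis plan does not need this. The FAS is everyone randomised. The PPS removes eligibility failures and significant deviators at the analysis stage, and SAP 5.2 tabulates significant deviations within the FAS. The FAS and PPS comparison tells the reader nothing about a subject whose outcome was never collected.

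The rule can still operate although enrolment has closed. Exclusion 3 (stable dose of muscle-active drugs) and exclusion 12 (no live vaccine) continue through the study. Because investigator nonadherence counts, a site error could remove a compliant subject.

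**Working it through.** **1. The two rules side by side**

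| | Protocol 11.2.2 | Protocol 4.2.1 |
|---|---|---|
| Force | mandatory | discretionary |
| Trigger | nonadherence adding significant risk; can include eligibility and GCP breaches | any eligibility failure; any noncompliance; other reasons |
| Stated aim | none | retain subjects |

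The 11.2.2 class is narrower, but an eligibility breach that adds significant risk falls under both rules.

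**2. What follows from withdrawal before the biopsy**

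- Visits after withdrawal: ET and safety follow-up only. Neither has a biopsy.
- DUX4 change from baseline: missing under SAP 8.2.
- Primary ANCOVA (Protocol 7.6.2, SAP 8.2): run on available values with no imputation, so the subject contributes nothing.
- SAP 8.2.1: the subject enters through baseline carried forward, placebo mean and observed worst case.

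A subject already biopsied loses no primary data.

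**3. The other two key endpoints for the same subject**

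SAP 4.4 places windows at midpoints between scheduled visits and allows withdrawal visits to be mapped.

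- TUG: Week 48 opens after (252 + 336)/2 = Day 294.
- MRI: Week 48 opens after (84 + 336)/2 = Day 210, or (168 + 336)/2 = Day 252 if a Week 24 MRI counts as a visit.
- Week 36 biopsy: the visit window runs to 252 + 14 = Day 266. A split visit may add up to 5 business days, giving about Day 273. Safety follow-up would then fall by about 273 + 7 + 3 = Day 283, still before Day 294.

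So for a pre-biopsy withdrawal with on-schedule visits, no ET or follow-up TUG maps to Week 48. An ET MRI can map to Week 48 only if the biopsy had been deferred to Week 36 and the MRI falls after Day 210 (or 252). Earlier TUG and MRI visits still enter the MMRMs. The primary ANCOVA has no earlier value to use.

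**4. Size**

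Inputs (Protocol 7.3 and 3.1.1): effect size 0.70, two-sided alpha 0.05, 80% power, 10% non-evaluable, 80 enrolled.

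The plan's figure reproduces. The two-sample t-test needs 33.02 per arm, rounded up to 34, or 68 in total. Then 68/0.90 = 75.6, rounded up to 76.

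Power by number evaluable (two-sample t-test, equal or near-equal arms):

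| Evaluable | Lost from 80 | Power, alpha 0.05 | Power, alpha 0.048405 |
|---|---|---|---|
| 80 | 0 | 87.1% | |
| 72 | 8 (the planned 10%) | 83.4% | 83.0% |
| 71 | 9 | 82.8% | |
| 68 | 12 | 81.2% | 80.8% |
| 67 | 13 | 80.6% | 80.2% |
| 66 | 14 | 79.97% | 79.6% |
| 64 | 16 | 78.7% | |

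The last column uses the lowest final alpha in SAP Table 12-1. The documents give no deviation rate, so the number withdrawn under 11.2.2 has to be assumed. One to four losses beyond the planned 10% would give 82.8% to 81.2%.

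**The case against.** The best defence is that a specific rule qualifies a general one: 4.2.1 gives a broad permissive list, and 11.2.2 requires withdrawal only where the subject is at significant added risk. Section 4.2.1 also contains a mandatory case, sponsor termination of the study. This stands to the extent that a reader who infers a strict contradiction goes too far. Section 4.2.2 does not contradict 11.2.2 either, since it concerns subjects who stop drug; the tension there is one of intent. But the specific-over-general reading leaves the mandatory rule in force, and the loss of outcome follows from that rule.

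A second objection is that the lost procedure is an invasive needle biopsy in a subject already at added risk. This stands in part. Where the deviation makes biopsy unsafe (anticoagulant use under exclusion 13, or a contraindication under exclusion 22), no wording recovers the DUX4 value. Only the remaining losses are avoidable.

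A third is that retaining a subject off drug may not help, because SAP 8.2 speaks of an on-treatment result. The half-life is about 10 hours (Protocol 1.3), and target engagement tracks concentration almost at once (3.2.1). Protocol 7.6.2, however, has the primary analysis use every available value on the FAS. The status of an off-drug biopsy is therefore unclear, and the fix has to settle it.

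Finally, the PPS criteria and the three imputation analyses show that the plan expects deviators and missing values. They limit the damage, but they do not replace an observed outcome.

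**Conclusion.** The point holds as a minor one. As written, 11.2.2 removes a randomised subject from follow-up where the section it cites would allow retention. Before the Week 16/36 biopsy, that removes the subject from the primary ANCOVA. The loss is avoidable only where the biopsy remains safe.

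The number affected is unknown and probably small. The documents give no deviation rate and do not say how many subjects had been biopsied when version 4.0 was issued. The 12 who had rolled over have no Week 36 biopsy due.

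A reader might infer that the trial's power is threatened, or that the comparison is biased towards one arm. The documents support neither: power stays above 80% down to 67 evaluable, and nothing indicates unequal deviation rates between arms. The power figures assume an effect size of 0.70 and equal or near-equal arms. What is at stake is avoidable loss of outcomes after randomisation.

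**What to change.** In Protocol 11.2.2, replace the mandatory withdrawal clause with: *may lead to discontinuation of study drug or withdrawal under Section 4.2; a significant deviation is recorded and assessed for PPS exclusion, and does not by itself end scheduled outcome collection for a consenting subject, except for any procedure the deviation makes unsafe.* Withdrawal for safety remains available under 4.2.1. The exception covers cases such as exclusions 13, 22 and 23.

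State also, in Protocol 7.6.2 and SAP 8.2, that a Week 16/36 biopsy taken after study drug is stopped counts in the FAS primary analysis, in line with the use of all available data.

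The change is short, but it is a protocol amendment needing IRB/IEC approval at up to 25 sites in five countries, so it should be carried in the next amendment. It also brings a few more follow-up visits and an investigator safety judgement before biopsy or MRI in these subjects. Off-drug biopsies may dilute the estimated effect slightly, which is the usual price of analysing subjects as randomised.
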